5.2 Secondary Outcomes

The secondary outcomes are measured as follows:

- The intratester reliability is evaluated by comparing size and position of the same receptive fields within 1 week detected by two different investigators.
- The intertester reliability is evaluated by comparing size and position of the same receptive field within 1 week detected by the same investigator.
- Influence of the stimulating system on phantom sensations and gait parameters is measured through the evaluation of a questionnaire concerning the phantom sensations, and through the analysis of a gait analysis (step width, step length, cadence, floor contact time and walking speed).

5.3 Other Outcomes of Interest

No other outcomes are measured and relevant to the study.

5.4 Safety Outcomes

As no safety objectives are planned in this study, no safety outcomes are recorded.

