3.4 Clinical Evidence to Date

To date there is no clinical research data available on the investigational product.

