4.4 Safety Objectives

As the safety of the detection method is out of discussion no safety objectives are set.

As the safety of the stimulation system has already been proven for the certification with the CE label, in this study we do not analyse safety aspects related with the use of the "Phantom Stimulator" (Cort X Sensorics, Spaichingen, Germany).

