9.2.4 Assessment of safety outcomes

9.2.4.1 Adverse events

In case of adverse events the event must be noted on the CRF. If the adverse event endangers the safety of the participant the testing must be stopped immediately.

In all cases the following information needs to be collected and recorded on the CRF: time of

onset, duration, action to be taken, relationship with study treatment.

9.2.4.2 *Laboratory parameters*

As there is no laboratory involved in this study, these parameters do not have to be assessed.

9.2.4.3 Vital signs

In this study, no vital parameters will be assessed as they are not of importance to the intervention. Further, as this study does not intend to change or affect any of these parameters, no assessment is necessary.

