11.4.5 Safety analysis

Not applicable.

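### Adverse events must be recorded on the CRF (9.2.4.1), but 4.4, 5.4 and 11.4.5 say safety is neither recorded nor analysed, so the study results have no planned summary of them

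*Combined protocol and SAP*

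**What the plan says.** Three sections set safety aside:

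- **4.4 Safety Objectives**, on finding the receptive fields: "As the safety of the detection method is out of discussion no safety objectives are set". On the stimulator: "in this study we do not analyse safety aspects related with the use". The reason given is that safety was already shown for the CE label.
- **5.4 Safety Outcomes**: "As no safety objectives are planned in this study, no safety outcomes are recorded".
- **11.4.5 Safety analysis**: "Not applicable".

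Other sections require safety data to be collected or passed on:

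- **9.2.4.1 Adverse events**, under the heading for assessing safety outcomes: "In case of adverse events the event must be noted on the CRF". It continues: "In all cases the following information needs to be collected and recorded on the CRF", and names onset, duration, action and relationship to study treatment.
- **12.1.2** counts an adverse events report among the source documents.
- **10.1.1** lists device malfunction and electrode-related skin irritation among findings that call for preventive or corrective steps.
- **10.1.2** requires health hazards needing action to reach the sponsor-investigator within 24 hours and the ethics committee within 2 days.
- **2.5** promises annual safety reports to the ethics committee and authorities.

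On earlier experience with the device, 3.4 says: "To date there is no clinical research data available on the investigational product".

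**The concern.** Two things looked wrong. First, the plan gives opposite answers to whether safety events are recorded. An investigator who follows 5.4 would leave blank the CRF entries that 9.2.4.1 requires. Second, where events are recorded, the plan states that they will not be analysed. That is an explicit choice and not just missing detail.

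At stake is what the results can say about tolerability. Section 3.7 describes the device and tests as carrying potentially no risk. The study collects data that could be set against that statement, but as planned they would not be. The analysis sets add to the problem, because they keep only participants who finish in conformity with the rules. Those stopped because of an event are the ones most likely to be missing.

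**Working it through.** The plan states no safety figure to reproduce, so the check is a comparison of sections. A short calculation follows for context only.

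**1. Are events recorded?** Section 5.4 says no. Section 9.2.4.1 says yes, with four data items in every case, and 12.1.2 agrees with it. Each section is complete in itself, so this is not damage from text extraction.

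**2. Are recorded events summarised?** Section 11.4.2 plans tables of field size and position, and a graph of field occurrence against time since amputation. Section 11.4.3 plans tables and graphs for reliability, gait and the questionnaire. Section 11.4.5 plans nothing. No planned output contains adverse events.

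**3. Who would be in the results?**
- Under 9.2.4.1, testing stops at once if an event endangers the participant.
- Under 11.4.1, only participants who complete in conformity are analysed, in both parts.
- Under 11.5, a participant is excluded if a whole meeting or more than 10% of the data is missing, and retained if less is missing.
- Under 8.5, a withdrawn participant's data may be kept or destroyed, case by case.

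Someone stopped for harm could therefore leave the analysed data. This is possible, not certain: 11.5 keeps participants with small gaps and does not say how the 10% is counted.

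**4. Does the information reach anyone?** Yes, in part. Health hazards needing action go out under 10.1.2, and annual safety reports under 2.5. Section 2.3 adds a duty to report unanticipated problems involving risk. Events below the threshold in 10.1.2 have no explicit expedited route.

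**5. Context: how much could a summary show?** If no event of a given type occurs among n participants, the one-sided 95% upper limit on its rate is 1 − 0.05^(1/n). The chance of seeing at least one event at true rate p is 1 − (1 − p)^n. The table takes p = 5% as an illustration.

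| n | Source | Upper limit, zero events | Chance of at least one event |
|---|---|---|---|
| 31 | recruitment target, 11.2 | 1 − 0.05^(1/31) = 9.2% | 1 − 0.95^31 = 0.80 |
| 28 | before dropout allowance, 11.2 | 1 − 0.05^(1/28) = 10.1% | 1 − 0.95^28 = 0.76 |
| 15 | assumed | 1 − 0.05^(1/15) = 18.1% | 1 − 0.95^15 = 0.54 |

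The figures 31 and 28 refer to the whole study. Only below-knee amputees with heel and forefoot fields at day 31 wear the device, and the plan does not give their number. The range shows that some recorded events are plausible, and that even a clean result would support only a modest statement.

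**The case against.** The strongest case against runs as follows.

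- **The omission is reasoned.** Section 4.4 gives CE certification as its ground, the study is risk category A, and 8.2.1 limits time with the working device to 1000 steps and ten 10-metre runs. This supports a light approach to safety. It does not explain why 5.4 contradicts 9.2.4.1, or why data already required should go unsummarised.
- **Outcome in 5.4 may mean endpoint.** The sentence does depend on there being no safety objectives. But it speaks of recording, and 9.2.4 uses the term safety outcomes for the adverse events it requires. The reading is possible, and the text should state it if it is meant.
- **Some harms are already analysed.** The questionnaire in 11.4.1 scores phantom pain, burning, cramping and similar sensations, and 11.4.3 compares them between ON and OFF with all single values shown. Worsening in these would be visible. Skin reactions, malfunctions and other events would not.
- **Dropout causes are covered.** Section 11.5 requires them to be analysed where data are excluded, and 9.2.5 records reasons for stopping. This stands, but it does not reach events in participants who finish.
- **Attribution to ON or OFF is limited.** The electrodes are worn in both conditions on one half-day. This stands, and the fix allows for it.

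A reader might infer that harms would go unreported altogether. The documents do not support that, given 2.3, 2.5 and 10.1.2. Nor is the list in 10.1.1 a list of expected device harms: it also contains pregnancies and implanted devices. Section 13 does not say what the publication will contain, and nothing forbids an adverse event listing.

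**Conclusion.** The point holds in a limited form. Sections 4.4, 5.4 and 11.4.5 conflict with 9.2.4.1 and 12.1.2, and adverse events that must be recorded have no planned summary in the study results. The completers-only analysis sets could also leave out a participant stopped for harm. The plan's routes to the sponsor-investigator, ethics committee and authorities remain in place.

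The primary and secondary results are unaffected, and no figure in the plan changes. This is an inexpensive improvement in consistency and reporting. It is worth making because 3.4 reports no clinical research data on the device. The conclusion does not depend on the upper limits shown above, which rest on an unstated part 2 size.

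**What to change.** Reconcile 4.4, 5.4 and 11.4.5 with 9.2.4.1 and section 10, so that they agree on what is recorded and what is summarised. If 5.4 means only that there is no safety endpoint, say so there.

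In 11.4.5, replace the present entry with text along these lines: *Adverse events recorded on the CRF, including skin irritation and any recorded device malfunction, will be listed and counted descriptively for all participants enrolled in part 1 and all participants exposed to the device in part 2, whether or not they complete. Results will be given by study part and, in part 2, by period of onset (ON or OFF). Skin events will also be counted per participant, because the electrodes are worn in both periods.*

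State that the conformity rule in 11.4.1 and the exclusions in 11.5 do not apply to this listing, and that adverse event records of withdrawn participants are kept for it despite the case-by-case rule in 8.5. A confidence limit is optional.

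The cost is one extra table and a few sentences, with no new visits or tests. The onset time needed for the ON/OFF split is already required. Section 9.2.4.1 sets CRF items only for adverse events and the CRF itself is a separate appendix, so check that it has a place for malfunctions.

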6. STUDY DESIGN

6.1 General study design and justification of design

The study with lower limb amputees is divided in two main parts and should incorporate 31 subjects.

The first part lasting 31 days, analyses the position and size of the receptive fields in a purely descriptive manner. Therefore, no randomisation, blinding or control group is needed.

The second part lasting 1 half-day, analyses the acute effect of a stimulation system (Phantom Stimulator, Cort X Sensorics, Spaichingen, Germany) on selected gait parameters and phantom sensations. Here the participants are randomized into two groups (AB or BA). As the design is a crossover, every subject serves as its own control and are single-blinded (unblinded investigators).

A schematic diagram can be found under 9.1 Study Flowchart.

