6.2.3 Other methods of minimising bias

As other methods to minimise bias we use all well-established and validated tests and measurement methods in the gait analysis. Further we analyse the selected method of receptive field detection on intra-/intertester reliability.

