9.2 Assessments of outcomes

9.2.1 Assessment of primary outcome

The primary measured outcome is the evolution/difference in size and position/movement of the detected receptive fields. This is done in the unit of cm^2 .

To record the data needed to compare the receptive fields is collected as follows:

- Day 1: detection of the receptive fields by one single tester at a self-selected time of day.
- Day 2: detection of the receptive fields at the same time of day as on day 1 by the same tester as on day 1.
- Day 7: detection of the receptive fields at the same time of day as on day 1 by the same tester as on day 1.
- Day 14: detection of the receptive fields at the same time of day as on day 1 by another tester as on day 1.
- Day 21: detection of the receptive fields at the same time of day as on day 1 by the same tester as on day 1.
- Day 28: detection of the receptive fields at the same time of day as on day 1 by the same tester as on day 14.
- Day 31: detection of the receptive fields at the same time of day as on day 1 by the same tester as on day 1.

The expression "same time of day" stands for:

-at maximum 1-hour difference in timing between the measurements.

-similar sleeping and dietary pattern 12 hours prior the measurement (assessed through a questionnaire).

The detection of the receptive fields is planned as follows:

- 1. performed by two specifically trained persons
- 2. performed through tactile stimulation of the skin surface with a brush (mild toothbrush or similar).
- 3. the receptive fields are determined through the dialogue with the participant. Here he can signal the presence of a receptive field with the word "Yes". Important in this setup is that the participant does not look at the inspected site or the tester.
- 4. the receptive fields are drawn on to the skin with a commercial eyeliner pencil.
- 5. the drawn receptive fields are photographed from different locations under standardized conditions (distance and angle).
- 6. this photo is imported in the program Photoshop (Adobe Photoshop Version 2017.1.1) where the respective area and position can be determined.

As a change in size is defined as a difference of more than 10% when comparing the same receptive field of two separate times.

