9.3.3 Meeting 2 (day 2, 1h)

• Detection of the receptive fields at the same time of day as on day 1 by the same tester as on day 1

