9.3.5 Meeting 4 (day 14, 1h)

• Detection of the receptive fields at the same time of day as on day 1 by another tester as on day 1

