11.4.3 Secondary Analyses

A secondary analysis concerning the inter- and intratester reliability is performed by the principal investigators ([name], [name]) at the end of the first part of the study (day 31). Here the days 1 and 2 are compared for intertester reliability and the days 28 and 31 are compared for the intratester reliability.

The secondary analysis concerning the intervention period (single day after day 31) is as well performed by the principal investigators ([name], [name]) after completion of the last gait analysis. Here the recorded gait parameters as well as the questionnaires are evaluated on changes originating between randomization A and B.

In both cases graphs and tables will be generated showing the mean, standard deviation, change as well as all single values of the participants.

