12.2.4 Electronic and central data validation

OptoGait: through proper setup and calibration (as written in the user's manual) prior to every measurement, and presence of at least 2 different investigators while performing the analysis.

Questionnaires: through evaluation by at least 2 different investigators and comparison of the

results.

Photoshop measurements: the measurements of size and position are performed 3 times by 2 different investigators and the mean value is considered.

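### Part 1 waives blinding and plans no masking of testers or photo readers, so day 1 v 2 agreement may be overstated and change over time cannot be separated from tester memory or leftover skin marks

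*Combined protocol and SAP*

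**What the plan says.** Section 6.1 describes part 1 as description only and draws the consequence: "Therefore, no randomisation, blinding or control group is needed".

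Section 9.2.1 sets out the mapping. The tester strokes the skin with a brush, the participant signals a field verbally, and "the receptive fields are drawn on to the skin with a commercial eyeliner pencil". The outline is photographed and measured in Photoshop. The one safeguard during mapping concerns the participant: "Important in this setup is that the participant does not look at the inspected site or the tester".

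Sections 9.1 and 9.3 give the tester sequence for days 1, 2, 7, 14, 21, 28 and 31 as A, A, A, B, A, B, A. For day 2 the text is "Detection of the receptive fields at the same time of day as on day 1 by the same tester as on day 1"; for day 14 it is "Detection of the receptive fields at the same time of day as on day 1 by another tester as on day 1".

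For the photographs, section 12.2.4 states that "the measurements of size and position are performed 3 times by 2 different investigators and the mean value is considered". Section 6.2.3 offers one bias control for the mapping: "Further we analyse the selected method of receptive field detection on intra-/intertester reliability".

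**The concern.** Describing a quantity does not protect it from observer bias, and part 1 does more than describe. Section 11.1 states null and alternative hypotheses on change in size and position and on reliability, section 11.2 bases the sample size on a paired t-test at the 5% level, and the synopsis lists reliability among the primary outcomes.

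The measurement depends on judgement, because the tester decides where to stroke and where to draw the line. Tester A returns about 24 hours after drawing the first outline. The plan does not have A work without the earlier photographs or data sheets, does not have the pencil removed, and does not have the skin checked before the next mapping. If day 2 is pulled towards day 1, agreement between the two looks better than the method deserves. A reader would then judge later change against an error that is too small. The primary result, the time course itself, would be mixed with whatever the tester remembers or can still see.

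**Working it through.** **1. Which comparisons are exposed.** From the tester sequence in sections 9.1 and 9.3:

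| Comparison | Testers | Exposure to the tester's own earlier map |
|---|---|---|
| Day 1 v 2 | A, A | strongest: 1 day apart |
| Day 1 v 7 | A, A | present, weaker |
| Day 1 v 21, 1 v 31 | A, A | depends on how memory behaves |
| Day 1 v 14, 1 v 28 | A, B | tester difference mixed with time |
| Day 28 v 31 | B, A | not the same route: different testers |

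Section 11.4.3 says "Here the days 1 and 2 are compared for intertester reliability", but the schedule has one tester on both days. I follow the schedule; the reversed labels are a separate matter.

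**2. Marks follow a different clock.** Marks carry over from the previous mapping, not from day 1. The gaps between mappings are 1, 5, 7, 7, 7 and 3 days. Day 31 comes 3 days after day 28, the second-shortest gap, so leftover marks would not simply fade across the study.

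**3. What the safeguards cover.** The participant's looking away does not mask the tester and applies only during testing. Averaging three readings by two investigators reduces random reading error; an expectation shared by the readers survives the averaging. The reliability analysis named in section 6.2.3 uses day 1 v 2, the pair most exposed, so it cannot reveal the problem. Access to earlier records is open: section 12.2.2 lets every investigator on the clinic's intranet reach the data, and the section 11.4.1 data sheet puts all days for one field on one sheet.

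**4. Illustration of direction.** The documents give no mapping error, so there is no plan figure to reproduce. The only plan input is the 10% size rule (section 9.2.1). Everything else here is assumed: the true field never changes; each independent mapping has an error with a coefficient of variation CV; an anchored tester's error is w × (error of the earlier map) + (1 − w) × (fresh error).

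With anchoring to day 1, the SD of the difference from day 1 is approximately CV × √2 × (1 − w), and the share labelled changed is 2 × [1 − Φ(10 / SD)].

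- Independent mapping, CV 10%: SD = 10 × 1.414 = 14.1; 10 / 14.1 = 0.707; share 48% at every visit.
- Day 2, w = 0.7: SD = 14.14 × 0.3 = 4.24; 10 / 4.24 = 2.36; share about 2%. Simulating the ratio of sizes (400,000 draws) gives 2.5%, shown below as 3%.
- Day 31, w falling from 0.7 at day 2 with a 7-day half-life: w = 0.7 × 0.5^(29/7) = 0.04; SD = 14.14 × 0.96 = 13.6; 10 / 13.6 = 0.736; share 46%.

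Simulated shares labelled changed from day 1, tester A visits, CV 10%, starting w = 0.7:

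| Form of anchoring | Day 2 | Day 7 | Day 21 | Day 31 |
|---|---|---|---|---|
| None (independent mapping) | 48% | 48% | 48% | 48% |
| To day 1, fading | 3% | 22% | 43% | 46% |
| To own previous map, constant | 3% | 11% | 19% | 25% |
| To day 1, constant | 3% | 3% | 3% | 3% |

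For fading anchoring with CV 5 to 15% and starting w 0.3 to 0.7, the share runs from 0 to 50% at day 2 and from 14 to 63% at day 31. With independent mapping it is 16 to 64% at all visits.

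**5. Reading.** Low apparent change at day 2 appears under every form of anchoring tried. A rise with time appears under two of the three; constant anchoring to day 1 gives a flat line and would hide real movement at every tester A visit.

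**The case against.** The strongest reply is that the documents are silent rather than wrong. They do not say that testers consult earlier maps, that eyeliner persists, or that readers know day and tester. The testers are described as specially trained, and the CRF and other appendices are supplied separately and cannot be seen here. This stands as a limit: the conclusion is that no masking is planned, not that bias has occurred. It does not remove the point, because section 6.1 waives blinding expressly and for a reason that section 11.1 contradicts.

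A reader might infer that apparent change must grow with time. The documents do not support that. Tester A maps on days 1, 2, 7 and 21 before day 31, so memory is refreshed, marks follow the gaps in step 2, and constant anchoring gives no growth. A reader might also extend the worry to every short retest; day 28 v 31 compares B with A, so recall of one's own map does not apply in the same way. Nor does the primary objective look for increasing change: section 4.2 asks how the fields behave.

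It is also fair to say that masking files cannot erase what a tester recalls after 24 hours, and that tracing a drawn line leaves less room for expectation than drawing it. Both stand. The fix closes the avoidable routes, not all of them.

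**Conclusion.** The concern holds in a limited form. The plan waives blinding in part 1 for a reason that does not fit its own hypotheses, and provides no masking of testers or readers and no removal of marks. Day 1 v 2 agreement may be overstated, day 1 v 7 less so. The time course cannot be separated from tester memory or residual marks, and the bias could create a trend or conceal change.

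Its size cannot be derived from the documents. The shares above show direction and rest wholly on the assumed CV and anchoring weights. The required sample size is unaffected. Because independence lost at mapping cannot be restored in the analysis, and the remedy is cheap, the change should be made.

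**What to change.** Replace the sentence in section 6.1 with one saying that part 1 needs no randomisation or control group, but that mapping and photo reading are masked as far as practicable. Then add to sections 9.2.1 and 12.2.4:

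1. After photographing, all marks are removed; clear skin is confirmed and recorded before each mapping.
2. The tester maps without access to earlier photographs or data sheets.
3. Photographs carry a random code hiding day and tester. Each outline is traced on its own coded image, in random order, and codes are broken only to compute size differences and overlap. An existing team member who does not read the photographs holds the code list.

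State as a limitation that the same tester's recall, especially from day 1 to day 2, remains.

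Cost: protocol wording, wiping the skin, renaming files and keeping a code list. Testers, readers, visits and sample size do not change. The downside is slightly more file handling.

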6.2.2 Blinding procedures

The blinding of the participants is ensured as there is no visible difference between the two groups as well as through standardised questions and talking patterns of the investigators so not to reveal any relevant information.

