6.3 Unblinding Procedures (Code break)

The codes for the unblinding procedures are stored in sealed envelopes which can be opened only by [name] or [name].

This procedure can take place in case of suspension/exclusion from the study, premature study termination, explicit requests from part of the CC or in case of individual analysation of the data because of health issues or threats to the participant.

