7.3 Assignment to study groups

The participants are assigned into the 2 possible sequences of the second part of the study in randomised order by block randomisation with a block size of 2 patients. This randomisation is performed by the principal investigator as soon as two patients are available. These are then randomized with the computer program Excel.

After this process, the assigned sequence is communicated to the responsible investigator for the patient and marked on the CRF. The patient is unaware of the study sequence until the study is terminated completely.

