8.2 Administration of experimental and control interventions

8.2.1 Experimental Intervention

The experimental intervention concerns only the second part of the study. In the first part, a purely descriptive evaluation of the size and position of the receptive fields over the timespan of one month (31 days) is performed.

During the second part of the study, which is performed in one day, the certified medical device Phantom Stimulator (Cort X Sensorics, Spaichingen, Germany) is tested upon its effects on selected gait parameters and phantom sensations.

During the experimental intervention, the participants are setup with the device and are given an instruction. Further they are asked to walk 1000 steps with the functional device and to perform a gait analysis.

The time spent by the participants with the functional device is therefore restricted to 1000 steps and 10 times 10 meters of gait analysis.

Information on the medical device is given in section 8.1 and in the attached user manual.

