9.2.2 Assessment of secondary outcomes

The Intra-/intertester reliability of the proposed detection method as secondary outcome is assessed by comparing the size and position of the detected receptive between two different testers. Here the sizes and positions are compared and the deviations calculated. The detection takes place as described in section 9.2.1.

The influence of the Phantom Stimulator on gait parameters and phantom sensations is assessed through a gait analysis (OPTOGait, Microgate S.r.I, Italy, 2010) and a self-made questionnair.

After the conclusion of the first descriptive part of the trial, the participants qualifying for the Phantom Stimulator are tested. These tests are performed in one single day.

This day is planned as follows:

- first (for familiarization): Walking for 1000 Steps with a step counter, questionnaire and 10 runs of gait analysis
- second: The Phantom Stimulator (Cort X Sensorics, Spaichingen, Germany) will be installed
- third: Participants will perform A or B in a randomized and balanced order:
 - A. walking with the functioning (ON) Phantom Stimulator (1000 steps), questionnaire and 10 runs of gait analysis
 - B. walking with the unfunctional (OFF) Phantom Stimulator (1000 steps), questionnaire and 10 runs of gait analysis

For gait analysis, subjects will be walking in maximally possible self-selected speed for 10 runs (both directions are analyzed).

The recorded parameters during the gait analysis are:

- Step width
- Step length
- Ground contact time
- Cadence
- Walking speed

The 1000 steps during the familiarization and testing phases are recorded/controlled through a pedometer (Omron Walking Style One 2.0, Mannheim, Germany).

The questionnaire evaluating the short-term effects of the Phantom Stimulator on phantom sensations addresses the existence of these sensations and their nature with a VAS from 0-10 and is performed directly after the 1000 steps (right before the gait analysis).

For this phase of the study we calculate approximatively 4 hours. The "Phantom Stimulator" is worn during approximatively 3 hours.

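### Part 2 leaves every investigator aware of ON or OFF, although the second investigator already required at the gait analysis could be kept unaware there

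*Combined protocol and SAP*

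**What the plan says.** Section 6.1 describes part 2 as a crossover in which "every subject serves as its own control and are single-blinded (unblinded investigators". On assignment, section 7.3 states: "This randomisation is performed by the principal investigator as soon as two patients are available". It continues that "the assigned sequence is communicated to the responsible investigator for the patient and marked on the CRF", while the participant stays unaware until the study has ended. Section 6.3 adds: "The codes for the unblinding procedures are stored in sealed envelopes which can be opened only by" two designated people, and it ties opening to code-break events.

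The stated protection is in 6.2.2: the two conditions look the same, and there are "standardised questions and talking patterns of the investigators so not to reveal any relevant information". Section 8.2.1 says that "the participants are setup with the device and are given an instruction", without saying by whom.

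For the gait outcomes, "subjects will be walking in maximally possible self-selected speed for 10 runs (both directions are analyzed" (9.2.2). Phantom sensations are rated on 0-10 scales, nine of them in the dataset table of 11.4.1, directly after the 1000 steps and just before the gait test. The questionnaires are on paper (12.2.3) and are listed among the materials for patients (section 17).

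On staffing, 12.2.4 requires for OptoGait the "presence of at least 2 different investigators while performing the analysis". For questionnaires it asks only that two investigators evaluate them. Section 8.4 describes one-to-one support throughout. The principal investigators analyse part 2 (11.4.3).

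**The concern.** This is the only randomised comparison in the study, and its outcomes can respond to how the participant is handled. OptoGait records objectively, but what it records is a maximal-effort walk on instruction. The questionnaire is self-report. Section 3.5 already expects the set-up to show positive effects. Someone who holds that expectation and knows the device is on may, without intending to, urge more or put questions differently than when it is off.

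Such an influence follows the device state, so it would be read as a device effect. A favourable A-B difference could then not be separated from investigator expectation.

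**Working it through.** The plan gives no figure on this point to reproduce. The check has three steps.

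**1. Who knows the state at each stage**

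| Stage | Source | Who is aware | Second person documented? |
|---|---|---|---|
| Randomisation | 7.3 | Principal investigator | Not applicable |
| Assignment | 7.3 | Responsible investigator; anyone reading the CRF | Not applicable |
| 1000 steps | 8.4, 9.2.2 | Investigator in attendance (6.1) | No; 8.4 says one to one |
| Questionnaire | 9.2.2, 12.2.4 | Who hands it out is not stated | No; two evaluate it afterwards |
| Gait analysis | 12.2.4 | Investigators (6.1) | Yes, at least two |
| Transcription to the CRF | 12.2.3 | Anyone who sees the sequence on it | Not applicable |
| Analysis | 11.4.3 | Principal investigators | Not applicable |

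No investigator is planned to be unaware at any stage. A second person is documented for one stage of the session, the gait analysis. Since 6.2.2 says the conditions look alike, that person need not learn the state by sight.

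**2. Whether the crossover removes the bias**

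Let τ be the true device effect, π1 and π2 the period effects, and β the mean shift in an outcome caused by the investigator's knowledge when ON rather than OFF. The expected ON minus OFF difference is:

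- sequence AB: τ + β + (π1 − π2)
- sequence BA: τ + β + (π2 − π1)

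With equal numbers per sequence, the average is τ + β. Balancing removes the period effect and leaves β in full.

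**3. What a given β would do (assumed values only)**

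Assume τ = 0, a two-sided 5% paired t-test per outcome, and b = β divided by the SD of the paired differences. The rejection probability is P(|T| > t(0.975, n−1)), where T is noncentral t with n−1 degrees of freedom and noncentrality b√n. For b = 0.2 and n = 28, the noncentrality is 0.2 × √28 = 1.06.

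| b (assumed) | n = 28 | n = 15 |
|---|---|---|
| 0 | 5.0% | 5.0% |
| 0.1 | 8.0% | 6.5% |
| 0.2 | 17.5% | 11.2% |
| 0.3 | 33.4% | 19.2% |
| 0.5 | 72.3% | 43.8% |

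The 28 is the pre-dropout number in 11.2, which was set for receptive-field change. The 15 is an assumption. The documents give neither b nor the number expected to enter part 2.

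**The case against.** The strongest reply is that single-blinding is openly declared, the outcomes are secondary, the study calls itself a pilot, gait is measured by instrument at an already maximal effort, and 6.2.2 standardises what investigators ask and say. Much of this stands. Declared single-blinding is a choice, not an error, and the talking patterns bear directly on cueing. But 6.2.2 offers them as protection of the participant's blinding. They make no assessor unaware, and they do not expressly cover tone or encouragement over ten maximal runs.

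A reader might also infer more than the documents support:

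- **That two investigators are present throughout, so full assessor blinding needs no extra staff.** Section 12.2.4 documents this for the gait analysis only; 8.4 points to one person elsewhere.
- **That aware staff administer the questionnaire and give the instructions.** Neither is stated. Self-completion fits the text at least as well, and 8.2.1 does not name who instructs. Involvement of an aware investigator in the instructions is implied by 6.1, 6.2.2 and 7.3 read together.
- **That the sealed codes serve no purpose.** They can still protect the participant's blinding and govern formal disclosure. The two sections sit awkwardly together, no more.
- **That differences in encouragement carry over in full into speed or cadence.** Only an induced shift in the outcome does so, and its size is unknown.

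Finally, an unaware assessor does not stop a participant from recognising ON by the evoked sensation. That is a separate route, and it is no reason to leave the investigator route open.

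**Conclusion.** The point holds in a limited form. Investigators in part 2 know the device state by design, the outcomes are effort-dependent or self-rated, and the crossover does not remove a bias tied to that state. For the gait test, the plan's own staffing allows an unaware investigator. For the 1000 steps and the questionnaire it documents no second person, so a separate arrangement has to be stated.

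The size is not derivable. The error rates in step 3 rest on assumed biases and sample sizes; they show sensitivity and are not evidence that bias of that size will occur. The change is worth making because it is cheap and protects the study's only randomised contrast. It is not a fatal flaw, and the primary, descriptive part is unaffected.

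**What to change.** Amend 6.1, 6.2.2 and 7.3:

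- One investigator receives the sequence and sets the device state out of view. The other is not told it, gives the scripted gait instructions and runs OptoGait. Whoever performs the randomisation cannot take the second role.
- The working CRF records only period 1 or 2. The sequence is kept separately and linked to ON/OFF once the data-entry check of 12.1.1 is complete. The tables in 11.4.1, now laid out by A and B, are filled after that link.
- The participant completes the paper questionnaire alone and hands it in closed. This needs no second person, and it keeps answers about evoked sensations from revealing the state to the unaware investigator just before the gait test.

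Reconcile 6.3 with 7.3 (sealed codes against a sequence written on the CRF). The sequence should reach the first investigator without opening the 6.3 envelopes, which are reserved for code breaks. Reconcile 8.4 with 12.2.4 (one-to-one support against two investigators).

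The cost is a small change in roles and CRF handling, with no added staff at the gait analysis. The remaining weakness is that a participant may recognise or reveal the ON state. With blocks of two, a sequence revealed for one participant also discloses that of the other in the block.
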